4. OBJECTIVES AND OUTCOME MEASURES/ENDPOINTS

RESEARCH QUESTION/AIM(S)

Aim: To test the feasibility and acceptability of a secondary care place-based intervention using a pilot study. The intervention focuses on four dimensions linked to the Labonte model.

- 1. Physiological impacts Health Check
- 2. Health behaviours Health Coaching
- 3. Psycho-social factors Community and public service assets
- 4. Wider determinants of health Community and public service assets

Questions:

- 1. Is the Intervention feasible and acceptable in terms of recruitment and attrition?
- Is it feasible to implement the intervention?
 (e.g., number and duration of contact visits, completion of data collection, completion of four intervention components, and number of community and public service assets offered, description of social background)
- 3. What are the participants perceived experiences and perceptions of the intervention?
- 4. What are the deliverers perceived experiences and perceptions of the intervention, including barriers and facilitators to delivery and perceived impacts?

Objectives

Primary Objective

To test the feasibility and acceptability of a secondary care place-based intervention focusing on four dimensions linked to the Labonte model.

- Physiological impacts Health Check
- 2. Health behaviours Health Coaching
- 3. Psycho-social factors Community and public service assets
- 4. Wider determinants of health Community and public service assets

Outcome Measures/Endpoints

- 1) To determine effective means of recruiting participants (recruitment and attrition)
- 2) To assess the feasibility of implementing the intervention (e.g number and duration of contact visits, completion of four intervention components, completion of data collection and number of community and public service assets offered, description of social background)

When, Who and How

Baseline, RN – CRF A and questionnaires
1 week EHAEquality Health Home Visit form
4 weeks EHA
Equality Health Home Visit form

	8 weeks EHA Equality Health Home Visit form
	12 weeks EHA Equality Health Home Visit form, questionnaire
Secondary Objectives	To explore the participants acceptability and perception of the
To explore the participants acceptability and perception of the intervention	intervention
Evalore the deliverers acceptability of the	2. Explore the deliverers

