8.2 Inclusion Criteria

To obtain person centred standards a series of professional and public, patient engagement sessions were arranged to develop and finalise the EQUALITY HEALTH-CVD protocol. Dedicated discussion groups' and 'one-to-one consultation meetings' with professionals and those with lived experience helped address any challenges and improved the quality of the protocol research design. The recommendations included narrowing the eligibility criteria to focus only on participants diagnosed with transient ischaemic attack, peripheral vascular disease and ischemic stroke NIHSS score of 5 and below. This will ensure that clinical input

after hospital discharge does not compound intervention results and reduces the burden of excessive healthcare support systems overwhelming the participants.

Patients -

- 1. (Identified as) Male and Female
- 2. ≥18–100 years of age
- History of ischemic stroke NHISS score of less than 5 And/or
- 4. History of Transient ischaemic attack And/or
- 5. Referral to Peripheral Vascular Clinic.
- 6. Capacity to consent
- 7. Willingness to partake in a qualitative interview at the end of the intervention

Equality Health Advisors for semi-structured interviews:

Undertaken the role of an Equality Health Advisor

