9. STUDY PROCEDURES

Schedule of assessments (0 month)

Participants in the study will undergo eligibility screening in three different settings. During emergency admission in GUH, as an inpatient at YYF or during a routine clinic at various sites. The participants care team will provide potential participants with a patient information sheet.

Baseline data

All participants will be consented by a delegated member of the ABUHB research delivery team. After consent the following questionnaires will be completed

- CASE REPORT FORM A
- PROMIS 10
- EQ-5D
- South Wales Social Wellbeing Scale

The questionnaires will be collected either by Microsoft forms if Wi-Fi is available or paper form and then transferred to an excel database.

The initial consultation of the intervention date and time be organised either during baseline data collection by the ABUHB research delivery team, or via telephone or email by the Equality Health Advisor.

(Follow Up 1) Equality Health- CVD Intervention (week 1) Initial Consultation

Consented Participants will be offered an initial face to face home based appointment where the Equality Health Advisor will provide place-based support focusing on four domains.

- 1. Physiological impacts
- Health behaviours
- 3. Psycho-social factors
- 4. Wider determinants of health
- **1.**The Equality Health Advisor will conduct the following physical tests:
- Blood Pressure and HR
- Height
- Weight
- BMI
- Waist Circumference

All physical test results will be recorded - if blood pressure is considered high: Hypertension: Systolic 140 mm Hg or higher or diastolic 90 mm Hg or higher the Equality Health Advisor will advise the participant to keep track of their blood pressure at home using an automated blood pressure monitor once a day at a different time of the day for a period of seven days. If blood pressure remains high after this time the participant will be advised to seek medical support at their registered GP surgery. If the participant does not own a blood pressure monitor, a monitor recommended by the British and Irish Hypertension Society blood pressure will be provided to the participant by the study team.

If a blood pressure reading is in the category of hypertensive crisis (180/100) the Equality Health Advisor will advise the participant to seek immediate medical support.

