9.2. Screening and Eligibility Assessment

Initial identification and eligibility of participants will be confirmed by the clinical team and supported by delegated ABUHB research delivery team.

Potential participants will obtain a Participant Information Sheet (PIS) (via various routes including in hospital setting, at a clinical appointment or posted out with the potential participants outpatient appointment letter.

Electronic screening logs will be kept and will include reason for non-participation. The reason for non-participation will be sought via the ABUHB research delivery team.

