12. STATISTICS AND ANALYSIS

12.1. Description of Statistical Methods

Questionnaires

The researcher will analyse and report response and completion rates to questionnaires, in addition to summarising descriptive variability in questionnaire outcomes.

Participant and Equality Health Advisor Interviews

Analysis of interview data will follow Braun and Clarke's thematic method and will include

- Data collection
- Data Management (using qualitative software)
- Data Analysis (familiarisation, generating codes, searching for theme, defining ad naming themes)
- Illustrative quotes will support findings

Equality Health Advisors Reflective Diaries

Analysis of reflective diaries will help understand the thoughts, feelings and experiences documented by the Equality Health Advisors over the study time period. These accounts will support findings

These points of interest are aimed to identify insights and problems that may occur before considering a full RCT.

Progression criteria

To recognise and acknowledge protocol success the following criteria will be applied using a green light system.

Criteria Progression	Green Light	Amber Light	Red Light
	Recruitment	and Attrition	
No of participants offered the intervention and declined uptake during the consent process	≤ 20%	≤ 50-74% Investigate reasons for refusal	≤ 75% Use Modify intervention Using 6 SQUID (Six-Step Quality Improvement Design)
Recruitment Rate	≥ 80% of the target number of participants recruited within the first 5 months.	50-79% of the target number recruited within the first 5 months. Implement additional recruitment strategy	49-0% of the target number recruited within the first 5 months. Reevaluate recruitment strategies and consider protocol modifications
Attrition Rate at the end of the study	25% Drop out Consider progression to RCT	Investigate reasons for dropout and implement retention strategies	75-100% Consider not proceeding with RCT funding bid submission
Follow up Completion	90-100% of participants complete the scheduled number of contact visits.	60-89% of participants complete the scheduled number of contact visits. Investigate barriers and enhance follow-up procedures.	< 75% of participants complete the scheduled number of contact visits Re-evaluate follow up strategy and consider protocol adjustments when considering future research.

Feasibility of Implementing the Intervention			

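### The red refusal light goes to modifying the intervention without first asking why people declined, and its single count cannot separate refusing the research from refusing the intervention

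*Protocol*

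**What the plan says.** The first row of the progression table in Protocol section 12.1 is defined as "No of participants offered the intervention and declined uptake during the consent process". It is called a number but graded in percentages, with no denominator given. Green is 20% or less. Amber is printed as ≤ 50-74%, with the action "Investigate reasons for refusal". Red is printed as ≤ 75%, with the action "Use Modify intervention Using 6 SQUID (Six-Step Quality Improvement Design".

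The next row, recruitment rate, is graded separately on the share of the target recruited in the first five months. Its red action is "Reevaluate recruitment strategies and consider protocol modifications".

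Section 9.2 states: "Electronic screening logs will be kept and will include reason for non-participation". Section 6 adds that the Study Operational Group receives reports that include a summary of those logs, and that the group helps inform protocol amendments. In section 4, Question 1 reads: "Is the Intervention feasible and acceptable in terms of recruitment and attrition".

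**The concern.** A person approached for this study can turn down two different things: the advisor's visits, coaching and signposting, or the research wrapped around them. The row adds both together. At amber the team must find out which it was. At red, where the answer matters most, that step is absent and the written action falls on the intervention.

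Question 1 reads recruitment as a sign that the intervention is acceptable, and the criteria are meant to inform a possible RCT. If refusal were high mainly because of research burden, timing or illness, the written rule would change something that the decliners had never received. The feature that put them off could pass unchanged into the next study.

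**Working it through.** The plan gives no figure to reproduce here. The check is a reading of the text plus simple arithmetic.

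**1. What the count contains.** Section 9 says "Consented Participants will be offered an initial face to face home based appointment", so consent to the study comes before any access to the intervention. Consent is followed by Case Report Form A and three questionnaires. Someone who wants the visits but not the forms can only decline, and is counted with those who do not want the visits. Eligibility also requires "Willingness to partake in a qualitative interview at the end of the intervention", but people unwilling to be interviewed may be logged as ineligible under section 8.3 and not as decliners, so nothing below relies on that criterion.

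**2. Amber against red.** Amber asks for reasons and red does not. Elsewhere in the same table, the red cells for completion of components, participant satisfaction and advisors' perceived impact each call for a re-evaluation, review or reassessment, and any change they mention is something to consider or a possibility. The refusal row has no such step or qualification.

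**3. Whether the recruitment-rate row would act as well.** Inputs:
- target of 20 (section 8.1);
- planned pace of 5 per month for 4 months (section 9.1);
- green recruitment at 80% or more of target within five months (section 12.1);
- red refusal read as 75% or more (assumption).

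Formula: offered = recruited / (1 − refusal).
- 20 / (1 − 0.75) = 80 offered, 80 − 20 = 60 declined, 60/80 = 75%: red on refusal.
- 5 × 4 = 20 recruited in four months, 20/20 = 100% of target: green on recruitment rate.
- At the lower edge of green: 0.80 × 20 = 16 recruited, 16 / 0.25 = 64 offered, 48 declined, 48/64 = 75%: again green on recruitment and red on refusal.

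The two rows can therefore disagree, and then only the refusal row calls for action.

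**4. How little the undivided count says about the intervention.** Let s be the share of the 60 declines that are not about the intervention. The documents give no value, so 25%, 50% and 75% are assumed. Intervention-related declines = 60 × (1 − s).

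| s (assumed) | Intervention-related declines | Of all 80 offered | Leaving out the other decliners |
|---|---|---|---|
| 25% | 45 | 45/80 = 56.3% | 45/(20+45) = 69.2% |
| 50% | 30 | 30/80 = 37.5% | 30/(20+30) = 60.0% |
| 75% | 15 | 15/80 = 18.8% | 15/(20+15) = 42.9% |

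The answer depends on the mix of reasons and on the denominator. The row fixes neither.

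**The case against.** The strongest reply is that a red light would not be read blind. Reasons are sought and logged whatever the colour, a weekly team discusses recruitment, and log summaries go to the group that helps inform amendments. This stands, and it lowers the severity. It does not change the written rule, because no progression row uses the logged reasons or makes the red action depend on them.

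Second, the cell says modify, and does so through a named six-step method. A reader might infer that the protocol orders a redesign with no look at causes. The text does not support that: it does not list the six steps, so a review of reasons within them can be neither assumed nor ruled out.

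Third, other rows can reach research burden. The recruitment-rate row and the data-collection row both mention possible protocol changes. They have separate triggers, so they may help but do not ensure it. It would be too strong to say that the research burden will stay unchanged.

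Fourth, a reader might take the 18.8% above to mean that a red row can conceal refusal the table would call green. That is not supported. It needs the highest assumed share, and it keeps 45 people whose view of the intervention is unknown in the denominator as if they had accepted it. Without them the figure is 42.9%.

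Finally, the study is descriptive with 20 participants, this red cell does not itself stop progression, and an analysis plan not shown could tabulate refusals by reason. All true. The point is confined to the action that this table states.

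**Conclusion.** The concern holds as a minor point. The declined-uptake row uses one undivided count taken at study consent, and its red action goes to modifying the intervention without the reasons step that amber requires. The recruitment-rate row can be green at the same time, as with 20 recruited of 80 offered within five months. High refusal for research-related reasons could then lead to a changed intervention with the consent and data burden left alone.

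This rests on reading red as 75% or more. As printed, with a ≤ sign, red would overlap the other bands. The shares of refusal by reason are assumptions used only to show that the count cannot settle the question. They do not predict what this study will find.

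**What to change.** In the declined-uptake row of section 12.1:

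- Carry the amber step of investigating reasons into the red cell, ahead of any other action.
- Tabulate refusals by logged reason in three groups: intervention-related, research-related or other, and none given.
- Apply the 6 SQUID modification only when intervention-related refusals are the main driver, and say beforehand what counts as that. Otherwise the action is to review consent and data procedures.
- State the denominator, and report the result with the no-reason group counted both ways.
- Correct the printed direction of the red cut-off in the same edit, so that the trigger is clear.

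The cost is a reworded table row and some coding of log entries that are already collected. The drawback is that some decliners will give no reason. The result may then be a range, and a wide range could leave the choice of action to judgement.

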8. PARTICIPANT IDENTIFICATION

8.1. Study Participants

The sample size is 20 participants. In this instance, time and resource constraints make recruiting a larger sample challenging. While 20 participants may be smaller than the typical guideline of 30 suggested by (Billingham et al. 2013) it may still provide valuable insights.

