9.4. Discontinuation/Withdrawal of Participants from Study

Participants have the right to withdraw consent for participation in any aspect of the study at any time. The participants care will not be affected at any time by declining to participate or withdrawing from the study.

In this instance, participants who consent and subsequently withdraw should complete a withdrawal form with the researcher or delegated member of staff to determine and evidence the withdrawal request.

If a participant withdraws from the study, the research team will not attempt to recruit another participant. Once the target recruitment number of 20 participants has been reached, the study will be closed to recruitment.

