Follow up Completion	90-100% of participants complete the scheduled number of contact visits.	60-89% of participants complete the scheduled number of contact visits. Investigate barriers and enhance follow-up procedures.	< 75% of participants complete the scheduled number of contact visits Re-evaluate follow up strategy and consider protocol adjustments when considering future research.
Duration of visits	Average visit duration aligns with the planned schedule ± 10%	Average visit duration deviates from the planned schedule by 11-20%. Analyse time management and adjust visit plans if necessary.	Average visit duration deviates from the planned schedule by > 20%. Reassess visit structure and content.
Completion of Intervention Components	≥ 90% of participants complete all four components of the intervention.	75-89% completion rate. Identify and address barriers to the Labonte Model implementation	< 75% completion rate. Re-evaluate intervention design and implementation strategies.
Completion of Data Collection	≥ 95% of required data points collected	80-94% of required data points collected. Enhance data collection methods and follow-up.	80% of required data points collected. Implement corrective measures and consider protocol revisions.
Utilisation of Community and Public Service Asset	All planned community and public service assets are utilised as per individual goal plan	75-99% of planned assets are utilized. Identify reasons for underutilisation and adjust as necessary.	< 75% of planned assets are utilised. Conduct a thorough review and consider alternative assets or engagement strategies.
Participants' Acceptability and Perception			
Participant Satisfaction	≥ 80% of participants report	60-79% of participants report	< 60% of participants report

Perception of Effectiveness	high satisfaction with the intervention ≥ 80% of participants perceive the intervention as beneficial to their health and wellbeing.	high satisfaction. Investigate concerns and enhance the intervention based on feedback. 60-79% of participants perceive the intervention as beneficial. Address specific areas of concern to improve perceived effectiveness.	high satisfaction. Conduct a thorough review and consider major modifications to the intervention < 60% of participants perceive the intervention as beneficial. Re- evaluate the intervention's approach and content.
	Deliverers' Acceptal	oility and Perceived	Impact

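### The attrition and follow-up completion rows grade nested quantities on incompatible scales: with 9 to 14 of 20 lost, follow-up is red while attrition, the row that names the RCT, is not

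*Protocol*

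**What the plan says.** Protocol section 8.1 fixes the size: "The sample size is 20 participants". Section 9.4 rules out replacement: "If a participant withdraws from the study, the research team will not attempt to recruit another participant". The schedule in section 7 and the follow-up descriptions in section 9 put the last contact visit at week 12, and section 9.6 ends the study at the last follow-up of the last patient.

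The progression criteria in section 12.1 grade the following:

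- **Attrition, green:** "25% Drop out Consider progression to RCT".
- **Attrition, amber:** no percentage, only the action "Investigate reasons for dropout and implement retention strategies".
- **Attrition, red:** "75-100% Consider not proceeding with RCT funding bid submission".
- **Follow-up completion, green:** "90-100% of participants complete the scheduled number of contact visits".
- **Follow-up completion, amber:** 60 to 89%.
- **Follow-up completion, red:** "< 75% of participants complete the scheduled number of contact visits".
- **Data collection, green:** "≥ 95% of required data points collected". Amber is 80 to 94%.

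The follow-up row is printed twice with the same bands, once under recruitment and attrition and once under feasibility of implementation. No other row's actions name the RCT or the funding bid. Section 12.1 does not say how the colours of different rows combine into one decision.

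**The concern.** Recruitment and attrition form the first primary objective, and section 12.1 presents the criteria as a way to find problems before a full RCT is considered. Dropout and visit completion are not independent measures: each early dropout is also a participant who cannot complete the visits. If the two rows use cut-points that do not correspond, the same losses can be tolerable in one row and a failure in the other.

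The attrition row is the one that speaks of moving to, or holding back from, an RCT, and it is the more lenient of the two. Without a rule for combining rows, a team holding the results could cite either one.

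**Working it through.** **Inputs.** n = 20 (section 8.1); no replacement (section 9.4); last visit at week 12 (sections 7 and 9); bands from section 12.1. The protocol gives no power or precision calculation, so there is no figure of its own to reproduce. The check turns each percentage into a count out of 20.

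**Assumptions.** Both rows are taken as proportions of all recruited participants, since the table names no other denominator. Dropout means leaving before the week-12 visit. The attrition amber band is taken as what lies between the two printed figures.

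**Step 1, the bound.** Completion ≤ (20 − d)/20, where d is the number lost. Missed visits among those who stay can only lower it.

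**Step 2, the colours.**

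| Lost (d) | Attrition | Attrition colour | Maximum completion | Follow-up colour at that maximum |
|---|---|---|---|---|
| 2 | 10% | not amber or red | 18/20 = 90% | green |
| 5 | 25% | green | 15/20 = 75% | amber |
| 6 | 30% | implied amber | 14/20 = 70% | amber and red |
| 8 | 40% | implied amber | 12/20 = 60% | amber and red |
| 9 | 45% | implied amber | 11/20 = 55% | red |
| 14 | 70% | implied amber | 6/20 = 30% | red |
| 15 | 75% | red | 5/20 = 25% | red |

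Follow-up green needs at least 18 of 20, so at most 2 lost. The double colour at 6 to 8 lost arises because follow-up amber reaches down to 60% while red starts below 75%. If red was meant to be below 60%, follow-up red begins at 9 lost; if the 75% cut stands, it begins at 6. Attrition red begins at 15 either way.

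**Step 3, how often attrition red would appear.** With independent dropouts, P(red) = P(X ≥ 15), X ~ Binomial(20, p).

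| True dropout p | P(15 or more lost) |
|---|---|
| 50% | 2.1% |
| 60% | 12.6% |
| 70% | 41.6% |

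At p = 50%, the chance of 6 or more lost, which puts completion below 75%, is 97.9%.

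**Step 4, data completion.** The protocol does not define a required data point. As an assumption, give equal weight to the scheduled forms in section 7, counting the health check as one: 4 at baseline, 2 at week 1, 1 at week 4, 1 at week 8 and 6 at week 12. That is 14 per participant and 280 in all. If dropouts miss only week 12, the best case:

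- 5 lost: 1 − (5 × 6)/280 = 89.3%, below the 95% green threshold.
- 10 lost: 1 − (10 × 6)/280 = 78.6%, below the amber floor of 80%, while attrition is still not red.

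The first result is sturdy. With 25% lost, reaching 95% would need week 12 to hold at most 0.05/0.25 = 20% of all data points, against 6/14 = 43% here. The second is close to its threshold: with 50% lost, falling below 80% needs a week-12 share above 0.20/0.50 = 40%.

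**The case against.** Several points on the other side have force.

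- **Different criteria may show different colours.** Attrition green beside follow-up or data amber is ordinary in a traffic-light table, and no rule requires rows to match. This stands, so the 5-lost case alone would be a weak finding. It does not explain 9 to 14 lost, where a follow-up failure caused entirely by dropout is not a failure in the dropout row.
- **The follow-up row contradicts itself.** A reader might infer that 6 to 14 lost is always follow-up red. The text does not support that: at 6 to 8 lost the best-case completion is amber as well as red. The 25% boundary therefore rests on a cell that needs repair. The 9-to-14 range does not depend on it.
- **The lights are advisory.** A reader might infer that the table lets a failed pilot proceed, or that it stops at 75%. It does neither. Attrition amber calls for investigation and retention measures, red only asks the team to consider not proceeding, and all rows sit under the progression heading. The follow-up red action also refers to future research. What remains is that the only row naming the RCT does not speak against it until 15 of 20 are lost.
- **Extraction damage.** The missing sign beside 25% and the missing amber figure may have been lost in reading the table. Nothing should be built on a literal reading in which less than 25% dropout has no colour. The conflict is the same with or without the sign.
- **Consequences for the RCT.** A reader might scale up the RCT by the worst non-red loss, 1/(1 − 14/20) = 3.33 times the evaluable number. The documents do not say that an RCT would be planned on the pilot's raw attrition, least of all after retention measures.

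**Conclusion.** The point holds as an inconsistency between decision thresholds that the protocol itself fixes, so it is not a matter left to an analysis plan. Its firm core is 9 to 14 of 20 lost (45 to 70%): completion is at most 55 to 30%, red on any reading, while attrition is not red. At 6 to 8 lost the conflict depends on how the overlapping follow-up bands are resolved. At 5 lost, attrition green rules out follow-up green, which is a mismatch rather than a contradiction.

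This rests on recruited participants being the denominator in both rows and on dropout meaning loss before week 12. The data-completion figures support the point but rest on an assumed form count.

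Severity is should-fix. The study is a descriptive pilot with advisory lights, and no estimate is biased. The documents do not support the reading that a failed pilot is waved through; they support the narrower one that two linked rows can give opposite signals, with nothing to settle which one counts.

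**What to change.** Amend the table once, before results are known:

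1. Remove the 60 to 74% overlap between amber and red in follow-up completion, in both places where the row is printed.
2. Give attrition explicit inequality signs and a printed amber range. Start attrition red no later than the loss at which follow-up is necessarily red: above 25% (6 or more of 20) if the 75% cut stands, or above 40% (9 or more of 20) if red is meant to be below 60%.
3. If 25% loss is truly acceptable as green, move the follow-up and data-completion bands to match instead.
4. State how a red in one row bears on the RCT decision.

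The exact bands are for the study team to choose; the requirement is that the rows agree.

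**Cost.** A wording amendment to one table. The attrition light becomes less favourable, and with 20 participants tighter bands will miss green more often by chance. For example, if green were at most 2 of 20 lost, a true dropout of 10% would miss green with probability 1 − 0.677 = 32%. If red were 6 or more lost, a true dropout of 25% would give red 38% of the time. The team should accept those rates knowingly when it sets the bands.
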